9.0 OFF STUDY CRITERIA

This would occur if:

- A participant withdrew consent for any further data submission, or
- The participant was unable to complete the initial home visit procedures (e.g., unsuccessful blood draw), or
- Once a participant has completed all study assessments.

10.0 ADVERSE EVENTS

10.1 Expected Adverse Events

The CHIIP study is considered a low-risk educational and behavioral intervention study. The proposed home visits and biosample and data collection itself pose minimal risk to participants. Anthropometric measurements are all non-invasive. There would be a blood draw (thus potential for brief mild pain) associated with any home visit (1 to 2 over the course of the study for any given participant). The study team will ensure that the amount drawn at any visit is safe from a blood volume standpoint. It is possible, but unlikely, that some survey questions may cause participants to feel uncomfortable. All instruments proposed have been previously used in other research.

For participants selected to participate in the randomized intervention trial, it is possible that receipt of clinical lab results may cause some participants to feel uncomfortable or anxious. Similarly, receipt of a SCP with an individual's predicted cardiovascular risk may cause anxiety or discomfort. We will be monitoring self-reported anxiety and depression as part of our study. Prior CCSS studies have not shown that receipt of such survivorship care plans to be a source of significant anxiety.⁴³ We feel that providing such information, even when unexpected, may be important and have important future health consequences, as the research data to be provided to participants are all results with clinical interpretation and significance. For participants on the intervention arm, they will get a phone session or web video by which any results are given and explained to them by a survivorship trained clinician, approximating a normal clinical exchange. Participants on the control arm will only get a letter summarizing clinically relevant results, and will be encouraged to discuss any abnormal results with their primary healthcare provider. The study has in place, a process by which critical test results will be reported to the study team in real time, in which case, the PI or his designee, can notify the participant more quickly to seek medical follow-up. This process is similar to and adapted from that used by the CDC-sponsored NHANES for their in-person mobile assessments. For participants (either intervention or delayed control) with clinically actionable results but who have no current healthcare provider, the study team has access to resources to aid participants in finding providers in their area who have expertise in treating survivors of childhood cancer. This will be clearly explained on their results letter.

Otherwise, the only other anticipated risks would be related to participant privacy. The PI and study team will have clear and standard procedures to manage and protect individually identifiable private information. These include: appropriate human subjects research training for all staff with potential access to private information; technological safeguards such as use of encrypted data transmission between sites, secure password protection on computer servers; removal of identifiers at the earliest possible time and using separate unique study IDs instead; keeping any cross-walk files separate from the main analytic dataset(s); and avoiding showing individual data in any presentation or publication.

10.2 Monitoring and Recordings Adverse Events

As the CHIIP study is considered a low-risk educational and behavioral intervention, the FHCRC Data Safety Monitoring Committee, during the study's grant application, made an initial determination that overall data and safety monitoring can be overseen by the PI and the FHCRC IRB. All adverse events (expected or unexpected) will be reported to the FHCRC and St. Jude IRBs in accordance with the respective IRBs' policies.

11.0 DATA AND SAFETY MONITORING PLAN

The study will use the FHCRC Data and Safety Monitoring Committee (DSMC). The DSMC will review the summary of all adverse events collected as part of a protocol's data safety monitoring plan and reported by the PI at time of continuing IRB renewal, any expedited reports made to the IRB, and may refer protocols to the IRB for evaluation when modifications might be required to mitigate risks. The DSMC may also suspend or close the study based on review of the above information. The DSMC will review the accrual, patient safety, and other data at pre-specified intervals (at least annually), and make any determinations regarding interim analyses and stopping rules. On the basis of its review, the DSMC will provide a study with full approval (accrual continues, no changes), conditional approval (accrual continues but protocol changes required), suspension (accrual is stopped until protocol changes have been made but previously enrolled patients may continue the intervention), or closure (accrual is stopped and all interventions must stop).

12.0 DATA MANAGEMENT/CONFIDENTIALITY

The investigators will ensure that data collected conform to all established guidelines. Each participant has a pre-assigned CCSS ID number that will be used to protect subject confidentiality. Subjects will not be referred to by this number, by name, or by any other individual identifier in any publication or external presentation. Subject research files will be stored in a secure place (or database). Access is restricted to authorized personnel, with supervision by the PIs at FHCRC ([name]) and St. Jude ([name]). An existing data transfer/sharing agreement between FHCRC and St. Jude covers the exchange and sharing of existing and newly collated CCSS data. Data will not be shared with any other entity or outside investigators (external to those approved by CCSS) without approval by the relevant IRBs.

13.0 STATISTICAL CONSIDERATIONS

13.1 Aim 1 Analytic Plan

Hypothesis: Approximately 60% of participants will have an abnormal CV risk-factor finding that meets clinical intervention thresholds, and among those with abnormalities, 40% will be undertreated and 80% newly diagnosed.

Primary analyses: We will calculate the prevalence of hypertension, dyslipidemia, and diabetes by self-report and by physiologic measurement. We will then calculate the proportions (with exact 95% confidence intervals) of participants who may be underdiagnosed as well as the proportions undertreated (like **Figure 3**). We will calculate the prevalence of directly measured pre-diabetes separately. **Secondary analyses:** We will examine whether rates differ by: sex; current age; time since cancer diagnosis; obese ($BMI \geq 30 \text{ kg/m}^2$) vs. not; health insurance vs. not; recent history of being seen in a dedicated long-term follow-up clinic for survivors vs. not; and lifestyle factors (smoking, low fruit/vegetable intake, low physical activity).

Sample size considerations: Based on prevalence estimates from CCSS surveys and our pilot (**Table 2, Figure 3**), we expect ~60% of high CV risk participants ($n \sim 480$) to have an abnormal CV risk factor measurement; prevalence of individual risk factors ranging 20-40% (less when stratified by underdiagnosis/undertreatment status). With an overall sample $n=800$, we expect reasonable precision for our primary prevalence estimates (**Table 9**). Power to detect differences <10% in secondary analyses may be more limited.

TABLE 9. Estimated power for Aim 1 analyses.		
Prevalence \pm 95% CI	Minimum detectable proportions*	
N=800	N=320:480	N=200:200
5% \pm 1.5%	5% vs. 1/11%	5% vs. 0/14%
20% \pm 2.8%	20% vs. 12/29%	20% vs. 10/33%
50% \pm 3.5%	50% vs. 40/60%	50% vs. 36/64%

*2-sample Fisher's exact test, 80% power, $\alpha=0.05$.

Potential pitfalls / solutions: Our EMSI pilot achieved 60% enrollment. Funding from this proposal will enhance recruitment rates by providing an upfront (rather than conditional) participation incentive, which has been associated with higher rates of study participation.^{62,63} We will closely examine the demographic characteristics, past cancer treatment exposures, and self-reported burden of CV and other chronic conditions of survivors who are approached vs. not approached, and who ultimately participate vs. not. If differences are found, we will apply inverse probability weighting as a way to assess the sensitivity of our estimates.

13.2 Aim 2 Analytic Plan

Hypothesis: survivors randomized to the intervention will have a lower probability of having an undertreated CV risk factor compared with the control group at 1-year follow-up.

Primary analyses: We will describe baseline characteristics (including mean/median values of our target CV parameters) and proportions of underdiagnosis and undertreatment of our 3 CV risk factors. Our primary analysis will focus on the difference in the probability of having a CV risk factor undertreated after the 2nd home visit across the 2 study arms. As in Aim 1, undertreatment of hypertension, dyslipidemia, and diabetes at the 2nd home visit will be defined as blood pressure $\geq 130/80 \text{ mmHg}$, LDL ≥ 160 or triglyceride $\geq 150 \text{ mg/dL}$ (if fasting <10 hours: $\geq 200 \text{ mg/dL}$), or HbA1c $\geq 7\%$, respectively. Survivors with pre-diabetes at baseline will be undertreated at the 2nd home visit if fasting glucose $\geq 100 \text{ mg/dL}$ (non-fasting $\geq 140 \text{ mg/dL}$) or HbA1c $\geq 5.7\%$. As some survivors may contribute up to 3 outcomes (persistent hypertension, dyslipidemia, and diabetes/pre-diabetes), we will use generalized estimating equations (GEE), accounting for intra-individual correlation of the 3 outcomes, to estimate the overall intervention effect as a single parameter (3-element vector). If multiple survivors share the same primary healthcare provider (unlikely), we will apply random effects models in lieu of GEE given multiple

cluster types. Analyses will be conducted per intent-to-treat, and include all survivors with available end points.

Secondary analyses: In case survivors who were newly diagnosed (i.e., underdiagnosed) following their 1st home visit differ in their response to the intervention vs. those previously diagnosed but undertreated, we will examine estimates stratified by diagnosis status at the 1st home visit. For similar reasons, we also will examine estimates if pre-diabetes are excluded. In our primary model, we also will explore whether differences vary by sex, current age, time since cancer diagnosis, obese (BMI ≥ 30 kg/m²) vs. not, health insurance vs. not, and recent history of being seen in a dedicated long-term follow-up clinic for survivors vs. not. We also will explore, among intervention participants, whether action plan scores from the 4-month session are associated with differential undertreatment rates (as a single parameter). Finally, we plan to also compare across the study arms, the measured CV risk factor values from the 2nd home visit separately: 1) average systolic pressure, 2) average diastolic pressure, 3) LDL, 4) triglyceride, 5) blood glucose, and 6) HbA1c. For this subanalysis we will use linear models, adjusting for the value at the 1st home visit as a covariate.

Sample size considerations: Assuming 60% of Aim 1 participants (n=800) meet Aim 2 eligibility with a subsequent conservative 20% drop-out rate, ~380 survivors (190/arm) would have complete data. The study would be 80% powered ($\alpha=0.05$) to detect RRs ≤ 0.88 (i.e., $\geq 12\%$ reduction in the intervention vs. control group) if the prevalence of having an undertreated CV risk factor among controls after the 2nd home visit was 90% (10% reduction from baseline). If controls had an unlikely 50% reduction, we can still detect RRs ≤ 0.71 . Analyses stratified by initial underdiagnosis or undertreatment status (~75-150/arm) will be able to detect RRs ≤ 0.79 to ≤ 0.86 , respectively. Systematic reviews have reported RRs 0.6-0.8 for strategies similar our proposed interventions in the general population.^{64,65} For continuous outcomes (secondary analyses), we will be powered to detect change equaling $\sim 30\%$ of 1 standard deviation, which equates to 5 mmHg systolic blood pressure, 3 mmHg diastolic pressure, 10 mg/dL LDL, 30 mg/dL triglyceride, 10 mg/dL glucose, and 0.3% HbA1c. Differences within these ranges have been reported by others for interventions conducted in the general population.⁶⁶⁻⁶⁸

Potential pitfalls / solutions: We will closely monitor rates of abnormalities identified in Aim 1, as that influences the number of survivors eligible for Aim 2. As discussed earlier, we will oversample survivors known to have rarer target conditions (e.g., diabetes) such that the power to detect differences in Aim 2 is enhanced. Separately, given the nature of the intervention, participants and the study clinician cannot be blinded. However, exam staff will be blinded to randomization status.

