Study Objectives	
 1. To determine the prevalence of underdiagnosis and undertreatment of common cardiometabolic conditions (i.e., hypertension, dyslipidemia, diabetes) in survivors of childhood cancer at high-risk of future serious cardiovascular disease. 2. Among survivors who are found to be underdiagnosed or undertreated, to determine (via randomized clinical trial) the efficacy of a counseling/educational intervention to improve control of these cardiometabolic conditions. 3. Determine barriers on among survivors enrolled on the randomized trial and their primary healthcare providers that contribute to undertreatment of the study's targeted cardiometabolic conditions.
Study Design	Aim 1 is an observational study. Aims 2 and 3 are based on a randomized clinical trial design.
Population	Participants in the existing Childhood Cancer Survivor Study cohort who are classified as high-risk for future cardiovascular disease based on their demographic and cancer therapy exposures.
Primary Endpoints	Aim 1: Prevalence of underdiagnosis and undertreatment of hypertension, dyslipidemia, and diabetes. Aim 2: Probability of having an undertreated condition
Secondary Endpoints	Aim 3: Determine whether intervention and control arms differ in terms of survivor knowledge, self-efficacy, and medication adherence, as well as differences in their providers' knowledge and self-efficacy related to the care of childhood cancer survivors.
Type of control	Delayed intervention control (i.e., can choose to receive the intervention at the end of the study period).
Trial Blinding	Study staff performing home visits and study statisticians will be blinded. Participants and study staff delivering the counseling intervention cannot be blinded given the nature of the study.
Treatment Groups	Group A: upfront intervention group (30 minute counseling session focused on survivorship care plan, personalized action plan; 15 minute booster session at 4 months) Group B: delayed intervention control group (30 minute counseling session focused on survivorship care plan, personalized action plan)
Treatment Schedule	Baseline: educational materials (survivorship care plan, personalized action plan, and 30 minute counseling intervention 4 months: 15 minute booster session

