- **Diabetes:** American Diabetes Association classifies fasting blood glucose 100-125 mg/dL or HbA1c 5.7-6.4% as suggestive of impaired glucose tolerance (pre-diabetes). Similar to dyslipidemia, as fasting blood draws are not as commonly done in most primary care settings now for initial screening, for non-fasting (<8 hours) samples, blood glucose 140-199 mg/dL will be classified as suggestive of pre-diabetes if HbA1c was <5.7%. *Lifestyle intervention* is recommended (metformin prevention considered for select high risk populations).⁵⁴ Diabetes requires fasting blood glucose ≥ 126 mg/dL or HbA1c $\geq 6.5\%$. If not-fasting, random blood glucose ≥ 200 mg/dL would be concerning for diabetes if HbA1c was $<6.5\%$. In addition to lifestyle modifications, *metformin* is typically started with additional agents as indicated. We will ascertain the prevalence of pre-diabetes and diabetes; both may be eligible for Aim 2.

Undertreatment defined for each as:

- While any participant who was previously undiagnosed is also technically undertreated, we will reserve this definition to those who previously or currently reported to CCSS as being diagnosed with hypertension, dyslipidemia, or diabetes (either managed by lifestyle modifications or medication therapy), if their home-sampled value falls outside the recommended therapeutic range: blood pressure $\geq 130/80$ mmHg, LDL ≥ 160 mg/dL, triglyceride ≥ 150 mg/dL (if fasting <10 hours: ≥ 200 mg/dL), or HbA1c $\geq 7.0\%$ (different than the HbA1c diabetes diagnosis threshold⁶⁵).

3.3.2 **Primary Aim 2 Endpoint:** Probability of intervention subjects having an undertreated CV condition compared with the control group at 1-year follow-up.

3.3.3 **Primary Aim 3 Endpoint:** Barriers among survivors and their primary healthcare providers that contribute to undertreatment of hypertension, dyslipidemia, and diabetes.

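### The Aim 2 endpoint, hypothesis and power are per survivor, but the primary GEE is per condition, with an unsettled entry rule and no power of its own

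*Combined protocol and SAP*

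**What the plan says.** The synopsis gives the primary endpoint as "Aim 2: Probability of having an undertreated condition". Section 3.3.2 words it as "Probability of intervention subjects having an undertreated CV condition compared with the control group at 1-year follow-up". The hypotheses in 3.1.2 and 13.2 are likewise about survivors and their probability of having an undertreated risk factor.

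The sample size paragraph of 13.2 counts survivors: "380 survivors (190/arm) would have complete data". It continues "The study would be 80% powered ($\alpha=0.05$) to detect RRs" of 0.88 or lower if 90% of controls are undertreated at the second visit, and of 0.71 or lower if 50% are.

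The primary analysis in 13.2 changes the unit: "As some survivors may contribute up to 3 outcomes (persistent hypertension, dyslipidemia, and diabetes/pre-diabetes), we will use generalized estimating equations (GEE"), in order to "estimate the overall intervention effect as a single parameter (3-element vector"). No link function or working correlation is given.

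On which conditions count, 13.2 lists second-visit cut-points for blood pressure, lipids and HbA1c without reference to baseline status. It adds a pre-diabetes rule that applies only to survivors with pre-diabetes at baseline. It introduces the cut-points by referring back to Aim 1, where 3.3.1 says of undertreatment that "we will reserve this definition to those who previously or currently reported to CCSS as being diagnosed".

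**The concern.** A per-survivor and a per-condition analysis answer different questions. In the GEE a survivor with three abnormal factors supplies three outcomes. One who corrects one of two abnormal factors supplies one success and one failure, but under the endpoint as worded remains a failure. The RR from one analysis is not the RR from the other, and the stated power belongs only to the first.

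The entry rule adds a second ambiguity. The description of the outcomes as persistent, together with the pre-diabetes rule, points to conditions abnormal at the first visit. The other cut-points taken alone, and the three-element response, would admit any condition above threshold at the second visit. On that literal reading new hypertension would count but new pre-diabetes would not.

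This is the trial's primary efficacy result. While several versions remain open, the choice could be made after outcomes are known. A reader could also take a per-condition RR for the proportion of survivors helped.

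**Working it through.** **Inputs from the documents.** Section 13.2: "Assuming 60% of Aim 1 participants (n=800) meet Aim 2 eligibility with a subsequent conservative 20% drop-out rate"; control rates 90% and 50%; detectable RRs 0.88 and 0.71; α = 0.05; a detectable shift of about 0.30 SD for the secondary continuous outcomes. Sections 3.1.1 and 13.1: 60% with any abnormality, of whom 40% are undertreated and 80% newly diagnosed. Sections 2.2 and 13.1: individual factors at 20–40%. Table 9 names Fisher's exact test for Aim 1; no test is named for the Aim 2 power, so a two-sided Fisher test is assumed.

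**1. Reproduce the plan's power, one binary outcome per survivor.** 800 × 0.60 × 0.80 = 384, or 192 per arm, which the plan rounds to 190.
- 0.90 × 0.88 = 0.792. Exact Fisher power for 0.90 v 0.792 at 190 per arm is 80.5%.
- 0.50 × 0.71 = 0.355. Power for 0.50 v 0.355 is 79.5%.
- Stratified figures at a 90% control rate: RR 0.79 at 75 per arm gives 79.7%, and RR 0.86 at 150 per arm gives 81.1%.

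All four match 80% to within 2 points, with no input for conditions per survivor or within-person correlation.

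**2. Does multiplicity occur in this population?** A condition is either previously diagnosed or not, so a survivor in both the 40% and the 80% has at least two conditions. The minimum overlap is 40% + 80% − 100% = 20% of abnormal survivors. Section 2.2 reports such overlap in the pilot. Three prevalences of 20–40% sum to 60–120%; divided by 60%, that is 1.0 to 2.0 conditions per abnormal survivor.

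**3. How the two RRs separate, by hand.** Assumed: 60/30/10% of survivors have 1/2/3 abnormal conditions; conditions are independent; control persistence is 0.80 per condition; per-condition RR is 0.76 (intervention persistence 0.608, resolution 0.392); new onset is 0.15 per initially normal condition in both arms.
- Per condition: 0.608 / 0.80 = 0.76, power 99.8%.
- Per survivor, control: 1 − (0.6 × 0.2 × 0.85² + 0.3 × 0.2² × 0.85 + 0.1 × 0.2³) = 1 − 0.098 = 0.902.
- Per survivor, intervention: 1 − (0.6 × 0.392 × 0.85² + 0.3 × 0.392² × 0.85 + 0.1 × 0.392³) = 1 − 0.215 = 0.785.
- RR = 0.785 / 0.902 = 0.87, power 87.5%.

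The control rate here is the plan's 90%, and both versions exceed 80% power. With persistence 50%, new onset 30% and the same mix, the pair is 0.76 (81.5%) v 0.905 (38.9%). With one condition each and no new onset, the two versions coincide.

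**4. Illustration on the measurement scale.** Latent-normal model, 190 per arm, 30% per factor (which gives about 60% with any), benefit 0.30 SD. Assumed correlations: 0.2 between factors, 0.7 between visits.

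| Reading | Benefit in abnormal factors only | Benefit in all three factors |
|---|---|---|
| Each condition abnormal at visit 1, still abnormal | RR 0.77, 93% | RR 0.77, 93% |
| Survivor with any persisting condition | RR 0.81, 81% | RR 0.81, 81% |
| Survivor with any condition above threshold at visit 2 | RR 0.86, about 65% | RR 0.81, about 90% |
| All three conditions for every survivor | RR 0.82, 68% | RR 0.72, 97% |

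The first two rows involve only factors abnormal at visit 1, so the columns agree. The last two rows depend on whether initially normal factors also respond, which the documents do not say.

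**The case against.** The strongest reply is that 13.2 already leans towards one reading. Its outcomes are called persistent, only some survivors supply as many as three, and the three-element vector may mean no more than the maximum response length. The 90% control rate, described as a 10% reduction from baseline, presumes that everyone starts undertreated, which fails if all three conditions enter for every survivor. This stands: the all-conditions reading is the least likely. It does not remove the mismatch with the endpoint wording, nor supply power for the GEE.

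Three stronger inferences are tempting, and the documents do not support them.

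- **That the trial is underpowered.** The planned GEE, on its likeliest reading, has about 93% power in the illustration, and no version of it is shown to fall below 80% at the plan's 90% control rate.
- **That the endpoint as worded is necessarily the weakest version.** This depends on confining benefit to factors abnormal at baseline. If the counseling affects all three factors, the any-condition survivor reading overtakes the any-persisting one, and the all-conditions reading becomes the strongest.
- **That the reference to Aim 1 makes the outcome depend on diagnoses reported at follow-up, which the intervention could alter.** Section 13.2 lists explicit second-visit cut-points and calls survivors with baseline pre-diabetes undertreated. It stratifies by diagnosis status at the first visit, which treatment cannot change. The reference most naturally concerns cut-points; one clarifying clause is enough.

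**Conclusion.** The point holds as an inconsistency in the definition of the primary result. Endpoint, hypothesis and power are per survivor; the primary analysis is per condition, has no stated power, link or working correlation, and has an unsettled entry rule. These facts come from the text and from reproducing the plan's RRs, assuming a two-sided Fisher test.

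The size of the difference is not derivable from the documents. In the illustration the RR is about 0.77 per condition, against 0.81 to 0.86 for any condition per survivor; power is 93% against about 65% to 90%. Those figures rest on the assumed correlations, 30% per factor, and a 0.30 SD shift that the plan gives as a detectable difference for secondary outcomes, not as an expected effect. What does follow from the plan is that at least 20% of abnormal survivors have two conditions, so the two versions cannot be treated as interchangeable.

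**What to change.** Make the synopsis, 3.3.2 and 13.2 agree on one primary estimand before outcomes are compared by arm. The version closest to 13.2 is: for each condition above its threshold at the first visit, whether it is above its existing second-visit threshold, whatever diagnosis is reported at follow-up. Restrict the GEE to those conditions, with condition-specific intercepts and one common arm effect, and state the link and working correlation.

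Restate the detectable RR and power for that analysis over a range of within-person correlation and of conditions per survivor. Keep the survivor-level RR for any undertreated condition as a named secondary, with the existing power figures, and report new-onset abnormalities separately. A survivor-level primary would also resolve the conflict, but would require replacing the planned GEE.

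The cost is a protocol amendment to the endpoint wording, revised analysis text and a recomputed power statement; no new data are needed. The downside is that new-onset conditions leave the primary analysis.

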7.0 TREATMENT PLAN

7.1 Treatment Plan Overview

7.2 Assignment of Study Group

Among those who meet eligibility criteria for primary aim 1 but not primary aim 2, participation will end after the 1st home visit. Similarly, if we adopt a tiered consent process, those who could be eligible for aim 2 but who do not provide consent to the randomized intervention portion of the study, their participation will end after the 1st home visit.

Among participants who meet eligibility for primary aim 2, there will be a computer randomization on a 1:1 basis to intervention: control assignment, with the control group eligible to receive the intervention on a delayed basis (following the 2nd home visit). The study's goal will be to review in-person collected test results in real-time (within 1-2 days of being received at St. Jude) and determine eligibility with randomization assignment the same day. Given the intervention, it cannot be blinded to

either participant or study clinician. Staff who perform the home visits and the study biostatisticians will be blinded to the study group assignment.

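### Section 13.2 specifies no adjustment for first-visit values in the primary Aim 2 GEE, giving up a small amount of precision that the collected data could supply

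*Combined protocol and SAP*

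**What the plan says.** Section 13.2 (Primary analyses) compares the arms on the probability that a risk factor is undertreated after the second home visit. A survivor may contribute up to three binary outcomes. A GEE that allows for correlation within a person is used "to estimate the overall intervention effect as a single parameter (3-element vector"). No covariate, link function or working correlation is named.

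First-visit information does enter in two ways. Pre-diabetes at baseline sets the glycaemic cut-off at the second visit. Calling the outcomes *persistent* conditions also suggests that first-visit status decides which outcomes a survivor contributes.

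The secondary analyses in 13.2 compare six continuous measurements between arms, and there the plan is explicit: "For this subanalysis we will use linear models, adjusting for the value at the 1st home visit as a covariate". Other secondary uses of baseline data are estimates stratified by diagnosis status and a search for effect modifiers. Neither adjusts the primary effect.

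Section 7.2 says "there will be a computer randomization on a 1:1 basis" and mentions no stratification factors. Under 7.2 the first-visit results are reviewed before assignment. Under 8.2 a participant whose lipid, glucose and HbA1c results cannot be obtained does not continue. The first-visit values should therefore be nearly complete among those randomised.

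**The concern.** The primary outcome is a dichotomised repeat of a measurement taken a year earlier. A survivor just above a cut-off at the first visit is more likely to be below it at the second than one far above. The model also pools three conditions with different cut-offs, so condition type may explain further variation. Section 13.2 treats the first-visit value as prognostic in its secondary models but does not say whether it enters the primary one.

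What is at stake is efficiency on the trial's main question, and clarity. If adjustment is intended, the covariates must be named before outcomes are seen, or it will look post hoc. If it is not intended, available precision goes unused.

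**Working it through.** **Inputs from Section 13.2.** "The study would be 80% powered" at α = 0.05, with sidedness not stated and two-sided assumed here. The planning case is RR 0.88 "if the prevalence of having an undertreated CV risk factor among controls after the 2nd home visit was 90% (10% reduction from baseline"). The alternative ("If controls had an unlikely 50% reduction") is a control rate of 50% with RR 0.71. Numbers: "conservative 20% drop-out rate, ~380 survivors (190/arm) would have complete data". Check: 800 × 0.60 × 0.80 = 384, or 192 per arm, stated as about 190.

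**Step 1: reproduce the plan's figures without adjustment.** For one binary outcome per survivor, the pooled normal formula is

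power = Φ[(d − 1.96·se₀)/se₁], with se₀ = √(2p̄(1−p̄)/n) and se₁ = √((p₁(1−p₁)+p₂(1−p₂))/n).

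- 90% v 79.2%: d = 0.108, se₀ = 0.0370, se₁ = 0.0366; power Φ(0.967) = 83.3%.
- 50% v 35.5%: d = 0.145, se₀ = 0.0508, se₁ = 0.0502; power Φ(0.907) = 81.8%.

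Fisher's exact test, which Table 9 names for Aim 1, comes closer to the stated 80%:

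| Per arm | Control rate | RR | Fisher power |
|---|---|---|---|
| 190 | 90% | 0.88 | 80.5% |
| 190 | 50% | 0.71 | 79.6% |
| 75 | 90% | 0.79 | 79.7% |
| 150 | 90% | 0.86 | 81.1% |

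All four stated figures are therefore consistent with a two-sided unadjusted comparison. One-sided testing gives about 89 to 91% and does not fit.

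**Step 2: effect of adjustment on variance.** Three correlated outcomes per survivor were simulated at 190 per arm, with 600 replicates per scenario, independence working correlation and person-clustered robust standard errors. The model was fitted with and without the first-visit value of each risk factor. Only conditions abnormal at the first visit counted. Assumed, because the documents do not give them: r from 0.3 to 0.8, between-factor correlation 0.2, and baseline prevalences of 40%, 30% and 25%.

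Ratio of adjusted to unadjusted variance of the risk difference:

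| Control rate, RR | r = 0.3 | 0.5 | 0.7 | 0.8 |
|---|---|---|---|---|
| 90%, 0.88 | 1.02 | 0.97 | 0.94 | 0.92 |
| 50%, 0.71 | 0.98 | 0.98 | 0.87 | 0.82 |

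The second decimal carries simulation error; 1.02 means no measurable gain. A repeat simulation under the same restriction gave reductions of about 0/2/6/8% at 90% and 2/5/12/16% at 50%.

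**Step 3: convert to power.** Put n = 190/ratio into the Step 1 formula.

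- 90%: ratio 0.97 gives n ≈ 196 and power 84.4%; ratio 0.94 gives n ≈ 202 and 85.5%. From 83.3%, that is 1.1 to 2.2 points.
- 50%: ratio 0.98 gives n ≈ 194 and 82.5%; ratio 0.82 gives n ≈ 232 and 88.6%. From 81.8%, that is 0.7 to 6.8 points.

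This applies a variance ratio from multiple outcomes to the plan's single-outcome formula, so it is approximate. Inside the simulation, several outcomes per survivor already put unadjusted power at about 94 to 95% in the 90% case, and adjustment added at most half a point there.

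**Step 4: the scale matters.** With a logit link at 50% and r = 0.7, adjustment moved the log odds ratio (absolute value) from 0.604 to 0.702 and its standard error from 0.180 to 0.196. Power rose from 93.2% to 96.0%. Adding covariates under a logit link therefore changes the quantity estimated and does not shrink the standard error. A marginal effect has to be named.

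**The case against.** The strongest reply is that nothing is broken. Under randomisation the unadjusted intent-to-treat comparison is unbiased, and its standard error already allows for chance imbalance. The power statement stands without adjustment. All of this is right. A reader might infer that the primary estimate is biased or the trial underpowered; the documents support neither.

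A second reply is that 13.2 is silent on covariates and does not rule them out, and that first-visit status already helps define the outcomes. This also stands: the accurate statement is that no adjustment is specified. Likewise, 7.2 does not mention stratification, which is weaker than saying there is none.

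A third reply concerns size. A reader used to linear models might expect much more: at r = 0.7, adjusting a continuous outcome makes 190 per arm act like 190/(1 − 0.49) ≈ 373. That does not carry over. The outcome is dichotomised, and counting only conditions already abnormal narrows the first-visit range. Reductions above 15% appeared only at r = 0.8 with the 50% control rate, which the plan calls unlikely, or at r = 0.7 to 0.8 if all three outcomes counted for every survivor. On that reading, with control rate 40% and RR 0.78 assumed, the ratios at r = 0.3/0.5/0.7/0.8 were 0.99/0.93/0.76/0.72, but the reference to persistent conditions points away from it. The true r could also be low. Visits are about a year apart, fasting is not required, and dried blood spots or participant-measured blood pressure may replace the standard measurements at the second visit (8.7).

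What remains is a gain that is modest or nil, at almost no cost.

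**Conclusion.** The point holds as an optional but worthwhile efficiency improvement. Section 13.2 specifies no adjustment for first-visit values in the primary Aim 2 GEE, uses them in its secondary models, and has them in hand before randomisation. At the plan's own 90% control rate the benefit is small and disappears at low r; it becomes material only if control-arm persistence is nearer 50% and r is high. These sizes rest on the assumed r, between-factor correlation and prevalences, and on reading the outcomes as limited to conditions abnormal at the first visit. They credit nothing to prior-diagnosis status, which the simulation did not include. The direction is less sensitive: a gain appeared at both control rates for r of 0.5 and above. The unstated link and effect scale should be settled in the same edit, because adjustment under a logit link would otherwise change the estimand.

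**What to change.** In the primary analysis paragraph of 13.2, pre-specify the following:

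- The primary GEE includes condition type (hypertension, dyslipidemia, diabetes/pre-diabetes), prior-diagnosis status, and the first-visit values that define the condition concerned. These are systolic and diastolic pressure for hypertension; LDL and triglyceride with fasting status for dyslipidemia; and glucose (with fasting status) and HbA1c for diabetes/pre-diabetes. Each set enters only for its own condition.
- The link function is stated.
- The effect is reported as a marginal risk difference and risk ratio by standardisation, with person-clustered robust standard errors. This matches the difference in probability in the primary analysis and the risk ratios in the sample size paragraph.
- The unadjusted GEE is kept as a supporting analysis.
- If shared providers lead to the random-effects alternative already in 13.2, the same covariates and marginal summaries apply.

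The cost is SAP wording. No extra data collection is needed, and the first-visit requirement in 8.2 means few or no participants should be lost for missing covariates. The sample size statement can stay as it is.
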